9 DATA PROCESSING AND STATISTICAL CONSIDERATIONS

9.1 Case Report Form

9.1.1 Electronic Data Capture

It is the responsibility of the investigator(s) to ensure the completeness and accuracy of the eCRF. One eCRF must be compiled for each subject participating in the study.

Data required for the analysis will be acquired and transferred electronically to a central database by means of an Electronic Data Capture system (the "EDC-tool"). The system operates over the Internet according to the principle of online data capture. Data entered by investigators or data managers into local computers are directly transferred over the Internet to a central database, without any permanent local storage.

High security standards for the transfer and storage of study data are guaranteed by the use of technologies, such as encrypted data transfer, firewalls and periodic backup to protect centrally stored data. Writing access to the system will be limited to authorized personnel and the system will automatically keep an audit trail of all entries and corrections to the eCRF. Training in the use of the EDC-tool will be provided by the CRO and local monitor.

The EDC-tool will comprise an eCRF, designed specifically for the present study.

The EDC-tool is operated under an electronic signature, consisting of the combination of an identification code and a password. In relation to the present study, passwords and electronic signatures will be distributed to users of the EDC tool, and used for entering, modifying, or viewing study data.

It is the responsibility of individuals who receive an electronic signature to keep their password secret, i.e., not to reveal it to third parties, and to access the EDC-tool, to enter or modify study data using the EDC-tool only under their personal identification code and password.

9.2 Data Management

The CRO is responsible for the data management of the study. The CRO will design the eCRF with the PI, conduct quality control and review of the eCRF, and create a Data Management Plan, including programming and validation of the database, user training, data handling and edit checks, data cleaning and query generation and processing, medical coding, SAE reconciliation and database closure. Key site and CRO personnel will be trained on the eCRF and the EDC system.

9.3 Statistical Analysis

9.3.1 Statistical hypotheses and methods

The primary hypothesis of the study is that Vitamin E and Omega-3 fatty acid (DHA EE) in combination will reduce hepatic fat fraction greater than placebo after 6 months of intervention in adults with NAFLD.

In general, continuous variables will be summarized with the mean, standard deviation, median and range. Categorical variables will be summarized with counts and percentages. SAS[®] version *9.4* or higher will be used to analyse the data.

9.3.2 Primary endpoint analysis

Decrease in hepatic fat fraction [%] relative to baseline between Vitamin E + DHA EE combination vs. placebo, measured by MRI-PDFF after 6 months of intervention. The decrease will be analysed with a linear mixed model with the hepatic fat fraction in % at 6 months as response variable. The hepatic fat fraction in % at baseline, treatment group and diabetes status will be included as fixed effects. Site will be included as random effect. This representation is formally identical to an analysis that uses the change in hepatic fat fraction in % (6 mos vs. baseline) as response variable and the hepatic fat fraction in % at baseline, treatment group and diabetes status as fixed effects and site as random effect [Laird, N. Further comparative analyses of pre-test post-test research designs. The American Statistician 1983, 37: 329-330; O'Connell, N. Methods for Analysis of Pre-Post Data in Clinical Research: A Comparison of Five Common Methods. Journal of Biometrics and Biostatistics, 2017. 8(1):1-8.]. However, this representation is chosen since it allows for easier variance-stabilizing transformations if necessary.

Statistical tests of significance will be 2-tailed at a 5% significance level. With blinded data, the residuals of the model will be analysed visually (QQ-plots, residual plots) to determine if the model assumptions (normality, variance, homogeneity) are met. If necessary, variance-stabilizing transformations will be considered.

9.3.3 Secondary endpoint variable(s) and analyses

- Differences in hepatic fat fraction [%], measured by MRI-PDFF after 6 months of intervention, between DHA and placebo will be estimated with the same model as the primary endpoint. The estimated difference will be displayed with its 95% confidence interval.
- Differences in hepatic fat fraction [%], measured by MRI-PDFF after 6 months of intervention, between Vitamin E and placebo will be estimated with the same model as the primary endpoint. The estimated difference will be displayed with its 95% confidence interval.
- Between group differences in anthropometric measures, after 3 and 6 months of DHA EE and/or Vitamin E intervention will be analysed with the same approach as the primary endpoint, using the relevant anthropometric measure at baseline as the respective baseline covariate and gender as a categorical covariate.
- Between group differences in inflammatory markers after 6 months of intervention and liver enzymes after 3 and 6 months of DHA EE and/or Vitamin E intervention will be analysed with the same approach as above and diabetes status as a categorical covariate included in the model.
- Between group differences in the FIB-4 score after 6 months of DHA EE and/or Vitamin E intervention will be analysed with the same approach as above.
- \circ Between group differences in plasma DHA and plasma α -tocopheryl after 3 and 6 months of intervention will be analysed with the same approach as above.
- Between group differences in SF-36 quality of life score after 6 months of DHA EE and/or Vitamin E intervention will be analyzed by ANCOVA with baseline score included in the model.
- Between group differences in dietary intake of LC-PUFA (i.e. DHA and EPA) will be assessed by the FFQ and analysed over time by repeated measures ANOVA with baseline level and site included in the model.

With blinded data, the residuals of the models will be analysed visually (QQ-plots, residual plots) to determine if the model assumptions (normality, variance homogeneity) are met. If necessary, variance-stabilizing transformations or non-parametric methods will be considered.

9.3.4 Exploratory variables

Transcriptome analysis of gene expression will be performed in peripheral blood mononuclear cells in a subset of (n=40) subjects (~10 subjects/ treatment arm). Changes in gene expression from baseline to end of treatment (6 months) will be examined. The analyses will be conducted by DSM. Briefly, differentially expressed genes will be analysed by ANOVA. The false discovery rate (q values) will be used to correct for multiple testing. Using the global gene expression profiling results, an extensive pathway analysis (e.g. MetaCore program and/or Ingenuity Pathway Analysis) will be conducted to better understand gene regulation, mechanisms of action and activated pathways by the various treatments in this NAFLD population.

Between group differences in plasma LC-PUFA-derived oxylipins will be analysed by ANCOVA using the relevant baseline oxylipin level as a covariate.

Sub-set analyses of PNPLA3, HSD17b and haptoglobin SNPs will be conducted on the Primary endpoint to assess potential genotypic responses to treatment.

9.3.5 Safety variables

All SAEs and AEs will be summarized by group. The number of subjects experiencing any events will be examined and the frequency of occurrence by system organ class will be tabulated using Medical Dictionary for Drug Regulatory Affairs (MedDRA) codes.

Vital signs, Hematology, Lipid panel, and Clinical Chemistry data will be summarized using descriptive statistics by group per timepoint including change from baseline at 6 months with group differences analysed using Least Squares Means and 95% Confidence Intervals.

A sub-set analysis will be performed in those with elevated baseline TGs to assess changes with the intervention over 6 months.

9.3.6 Compliance Analysis

A compliance analysis will be performed on all randomized participants who completed the study (6 mos) and ingested at least 80% of the study product using plasma DHA levels (μ g/ml) and plasma α -tocopheryl (μ mol/L) to confirm accuracy of the pill counts. ANOVA models will be employed with treatment as a factor. Frequency counts and percentages will also be presented for subjects who were at least 80% compliant by treatment group. Differences in this categorical outcome will be assessed using Fisher's Exact Test.

9.3.7 Sample size:

Le et al.[1] report that the variability (standard deviation) of the within-subject change in liver fat [%] for a period of 24 months in a similar population and with the same measurement method (MRI-PDFF) is 7%. Expecting a within-subject 3.64% absolute reduction in liver fat for the combination group vs. placebo [1, 2] and setting α =0.05 and 80% power, n=60/arm for the combination and placebo groups are needed (G*power 3.1.9.2, two-sample t-test).

To estimate the secondary endpoints (effect vs. placebo of the components (DHA EE alone and Vitamin E alone)) with a given precision (confidence interval width) of $\pm 3\%$ of liver fat, we need n=30/arm for the DHA EE only and Vitamin E only groups, leading to a necessary sample size of 180. With 10% expected attrition, the total sample size is 200 subjects.

Subjects will be stratified by Type II Diabetes diagnosis (no greater than 50% of sample). Subjects who withdraw prematurely from the study will not be replaced.

9.3.8 Study Populations

- The Intent-to-Treat (ITT) population will include all randomized subjects who receive at least one dose of study product, according to the product to which they were randomized. The primary efficacy analysis will be on the ITT population.
- The Per-Protocol (PP) population will include subjects who completed the study according to the protocol. The subject's data will be excluded from the per protocol analyses if the subject fails to meet one or more of the inclusion criteria at enrollment or meets one or more of the exclusion criteria. Data will be excluded if the subject has other significant protocol deviations or significant non-compliance with taking the study product (to be determined at a blinded data review meeting).
- The Safety population will include all subjects randomized into the study who received at least one dose of study product, according to the product they actually received.

9.3.9 Poolability of Data

It is considered that data will be pooled across sites for all analyses, unless significant deviations or imbalance in one or more sites is identified. Such discrepancies will be reviewed at the blinded data review meeting. Heterogeneity of the variability across sites will be investigated, and assumptions regarding the homogeneity of the variability across sites will be relaxed in the applied statistical model if necessary.

A statistical analysis plan (SAP) will be written by the statistician of the trial and will be finalized prior to database closure. The SAP will detail the handling of missing data and will outline all analyses to be conducted.

10 SAFETY

10.1 Definitions and Standards

Adverse Event (AE):

Any untoward medical occurrence in a subject involved in a clinical study administered an investigational product, whether or not related to this product.

An AE can therefore be any unfavourable and unintended sign (including an abnormal laboratory finding for example), subjective and objective symptom, or disease temporally associated with the use of a product, accidents, and whether or not considered related to the product or study-related procedure and reported by the subject or observed by the investigator.

Adverse Reaction (AR):

All noxious and unintended responses to a product related to any dose should be considered as AR. ARs are a subset of all suspected AEs for which there is reason to conclude that the investigational product caused the event.

Suspected Adverse Reaction (SAR)

SAR means any AE for which there is a reasonable possibility that the product or clinical trial material caused the AE. A SAR implies a lesser degree of certainty about causality than an AR, which means any AE caused by an investigational product.

Serious Adverse Event (SAE):

Any AE that at any dose fulfils at least one of the following criteria:

- Is fatal (results in death) (note: death is an outcome, not an event)
- is life-threatening

 (note: the term "life-threatening" refers to an event in which the subject was at risk of death at the time of the event; it does not refer to an event which could hypothetically have caused death had it been more severe)
- requires inpatient hospitalization or prolongation of existing hospitalization
 (*note*: "inpatient hospitalization" refers to an unplanned, overnight hospitalization)
- results in persistent or significant disability/incapacity

(*note*: the term means substantial disruption of one's ability to conduct normal life function)

• is a congenital anomaly/birth defect

(*note:* congenital anomaly/birth defect in offspring of subject taking the product regardless of time to diagnosis)

• is medically significant

(*note*: Medical and scientific judgement should be exercised in deciding whether expedited reporting is appropriate in other situations, such as important medical events that may not be immediately life-threatening or result in death or hospitalisation but may jeopardise the subject or may require intervention to prevent one of the other outcomes listed in the definitions above).

Suspected Unexpected Serious Adverse Reaction (SUSAR):

All suspected adverse reactions that are both unexpected and serious.

Unexpected Adverse Reaction:

An adverse reaction, the nature, or severity or incidence of which is not consistent with the applicable product information (e.g. Investigator's Brochure).

10.2 Adverse event assessment

Expectedness:

An unexpected AE is an event of which the nature or severity is not consistent with the applicable product information.

Causality Assessment:

The causality assessment of an AE to the investigational product will be rated as follows:

•	No (Not related):	The temporal relationship of the clinical event to product administration makes a causal relationship unlikely, or other drugs, therapeutic interventions or underlying conditions provide a sufficient explanation for the observed event.
•	Yes (Related):	The temporal relationship of the clinical event to product administration makes a causal relationship possible, and other drugs, therapeutic interventions or underlying conditions do not provide a sufficient explanation for the observed event.
•	Suspected	There is a reasonable possibility that the investigational product caused the observed event. Suspected implies a lesser degree of certainty about the causality of the observed event

Severity / Intensity:

The severity / intensity of AEs will be graded on a five-point-scale:

- Mild or Grade 1: discomfort noted, but no disruption to normal daily activities.
- Moderate or Grade 2: discomfort sufficient to reduce or affect normal daily activities.
- Severe or Grade 3: inability to work or perform normal daily activities.
- Life threatening or Grade 4
- Death or Grade 5

Outcome of event:

The outcome of an event will be classified as follows:

- Recovered
 - Recovered with sequelae
- Ongoing
- Fatal
- Unknown / Lost to follow-up

10.3 Safety Management

10.3.1 Procedures

All AEs occurring during clinical studies are recorded in the eCRF and are classified according to the Common Terminology for Adverse Events (CTCAE) system. AEs should be captured from the screening visit (V1) to the end of the study. Refer to the

https://ctep.cancer.gov/protocolDevelopment/electronic_applications/docs/CTCAE_v5_Quick_R eference_8.5x11.pdf_and_https://livertox.nih.gov/Severity.html, for additional information.

CTCAE Terms

An Adverse Event (AE) is any unfavorable and unintended sign (including an abnormal laboratory finding), symptom, or disease temporally associated with the use of a medical treatment or procedure that may or may not be considered related to the medical treatment or procedure. An AE is a term that is a unique representation of a specific event used for medical documentation and scientific analyses. Each CTCAE v4.0 term is a MedDRA LLT (Lowest Level Term).

CTCAE Grades

Grade refers to the severity of the AE. The CTCAE displays Grades 1 through 5 with unique clinical descriptions of severity for each AE based on this general guideline:

Grade 1 Mild; asymptomatic or mild symptoms; clinical or diagnostic observations only; intervention not indicated.

Grade 2 Moderate; minimal, local or noninvasive intervention indicated; limiting ageappropriate instrumental ADL*.

Grade 3 Severe or medically significant but not immediately life-threatening; hospitalization or prolongation of hospitalization indicated; disabling; limiting self-care ADL**.

Grade 4 Life-threatening consequences; urgent intervention indicated.

Grade 5 Death related to AE. Grade 5 (Death) is not appropriate for some AEs and therefore is not an option.

A Semi-colon indicates 'or' within the description of the grade. A single dash (-) indicates a Grade is not available. Not all Grades are appropriate for all AEs. Therefore, some AEs are listed with fewer than five options for Grade selection.

Definitions

A brief Definition is provided to clarify the meaning of each AE term. A single dash (-) indicates a Definition is not available.

Navigational Notes

A Navigational Note is used to assist the reporter in choosing a correct AE. It may list other AEs that should be considered in addition to or in place of the AE in question. A single dash (-) indicates a Navigational Note has not been defined for the AE term.

Activities of Daily Living (ADL)

*Instrumental ADL refer to preparing meals, shopping for groceries or clothes, using the telephone, managing money, etc.

**Self-care ADL refer to bathing, dressing and undressing, feeding self, using the toilet, taking medications, and not bedridden.

SAEs are reported in the eCRF and processed according to the applicable FDA requirements governing the conduct of clinical studies. All SAEs will be followed until resolution or at the latest 30 days after the subject's completion in the study.

SUSARs are reported and processed according to the FDA requirements governing the conduct of clinical studies.

When an unexpected SAE not previously listed in the Investigator's Brochure (IB) occurs in a multi-center clinical study, all investigational sites currently involved in the study should be notified by the study Sponsor or medical monitor within one week of receipt of the unexpected SAE.

SAE and SUSARs are also reported to a third-party vendor (referenced as Pharmacovigilance Vendor (UBC)) per flowchart below.

SAEs and SUSARs must be recorded on the electronic SAE Form. Following case processing, a US FDA MedWatch Form 3500A will be generated from the Pharmacovigilance Vendor for SUSARs. The event is entered into the PV safety database for filing and further expedited reporting by IND Sponsor-Principal Investigator.

The directions for completing the SAE Form are detailed in the "CRF Guidelines". This guideline will be available to all sites in the study.

For SUSARs, study treatment may be unblinded prior to reporting the case to the applicable regulatory authorities and IRB/IEC. Please see section 4.4 for unblinding procedures.

[figure not shown]
A Data Safety Monitoring Board (DSMB) will be arranged to review the safety information in the trial on a bi-annual basis. Details of the DSMB's responsibilities will be outlined in a DSMB plan.

SAEs will be reviewed by the safety officer of the study and the DSMB.

During or at the end of each study, an SAE reconciliation between data entered in the study database and the data entered in the pharmacovigilance database will be performed if any SAE has occurred in the study. All discrepancies found during the reconciliation are documented in an SAE reconciliation report and corresponding queries are sent to the investigators for clarification.

Since pregnancy is an exclusion criterion in the study, then for any case of pregnancy occurring during the conduct of the study, the course of the pregnancy and the outcome of both the mother and the offspring have to be documented in the eCRF and on the Pregnancy Form. This form will be provided to sites in the study, if needed.

The directions for completing the Pregnancy Form are detailed in the "Guidelines for Completing the Pregnancy Form". This guideline will be provided to sites in the study when needed.

10.3.2 Treatment and Holding/Stopping Rules for Drug Induced Liver Injury (DILI)

See the chart below for DILI monitoring and stopping guidelines:

Treatment Emergent ALT Elevation	Treatment Emergent Total	Liver Related	Management Recommendation
	Bilirubin	Symptoms	
Normal/near normal baseline: ALT ≥ 5 ×ULN Elevated baseline: ALT ≥3x baseline or ≥300 U/L whichever occurs first	Normal Patients with Gilbert's syndrome: No change in baseline total bilirubin	None	 Repeat ALT, AST, ALP, TBL, in 2-5 days. Follow-up for symptoms Initiate evaluation for other etiologies of abnormal liver tests
Normal/near normal	Normal	Severe	Repeat ALT, AST,
baseline: ALT ≥ 3 ×ULN Elevated baseline: ALT ≥2x baseline or ≥300 U/L whichever occurs first	Patients with Gilbert's syndrome: No change in baseline total bilirubin	fatigue, nausea, vomiting, right upper quadrant pain, tenderness, fever, rash, and/or eosinophilia (> 5%)	 ALP, TBL, in 2-5 days. Follow-up for symptoms Initiate evaluation for other etiologies of abnormal liver tests
Normal/near normal	Normal	None	Interrupt study drug
baseline: ALT ≥ ×8 ULN Elevated baseline: ALT ≥5x baseline or ≥500 U/L whichever occurs first	Patients with Gilbert's syndrome: No change in baseline total bilirubin		 Initiate close monitoring and workup for competing etiologies Study drug can be restarted only if another etiology is identified and liver enzymes return to baseline.
Normal/near normal baseline:	TBL > 2x ULN	Severe	Interrupt study drug
ALT ≥ ×3 ULN Elevated baseline: ALT ≥2x baseline or ≥300 U/L whichever occurs first	Patients with Gilberts syndrome: Doubling of direct bilirubin or increased INR to >1.5	fatigue, nausea, vomiting, right upper quadrant pain, tenderness, fever, rash, and/or eosinophilia (> 5%)	 Initiate close monitoring and workup for competing etiologies Study drug can be restarted only if another etiology is identified and abnormalities return to baseline.
Normal/near normal baseline:	Normal or Elevated	Severe	 Interrupt study drug Initiate close
ALT ≥ ×5 ULN		fatigue, nausea, vomiting,	 Initiate close monitoring and workup for
Elevated baseline: ALT > 3x baseline or > 300 U/L		right upper quadrant	competing etiologiesStudy drug can be restarted only
Drotocol no + 2017	Vorsion	Data	Dago 40 of 52

(whichever occurs first)	pain, tenderness, fever, rash, and/or eosinophilia (> 5%)	if another etiology is identified and abnormalities return to baseline.
-----------------------------	--	--

Source: Modified from Table 1 in REGEV et al, 2019 [36]

* If a patent lives in a remote area, laboratory testing can be performed locally, and the results should be promptly communicated to the investigator site

Study Stopping Rules:

The DSMB will review clinical safety data on an ongoing basis to identify potential safety issues arising during the conduct of the study. Including but not limited to the following:

- 1. 1 subject receiving the active treatment experiences a grade 5 CTCAE during the clinical trial that it is likely attributable to the study drug(s), OR
- 2. 2 or more subjects receiving the active treatment experience a grade 4 CTCAEs likely attributable to the study drug(s), OR
- 3. 3 or more subjects receiving the active treatment experience a grade 3 CTCAEs likely attributable to the study drug(s).

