6.4.3 Visit 3 (3mos Visit)

The following assessments are done during the 3 mos Visit:

- 1. Physical exam
- 2. Vital signs (heart rate, blood pressure)
- 3. Anthropometrics
- 4. FFQ (see Appendix 1)
- 5. Fasted Blood draws (>10 hours) for Clinical chemistry, CBC, Fatty Acid (DHA) and Vitamin E analyses
- 6. AUDIT Questionnaire Self- Report Version
- 7. AEs
- 8. Concomitant Medications
- 9. Compliance (pill count- subjects to return all used and unused cards in the kit)

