7.1.3 Blood sample assessment

Clinical chemistry: Glucose, HbA1c, ALT, AST, GGT, ALK-P, eGFR/creatinine clearance, creatinine, insulin, bilirubin, (**note:** for **ALT and AST** reference ranges for HH flags are to be used to determine clinical significance (CS))

Lipid panel: total cholesterol, HDL-cholesterol, LDL-cholesterol, oxidized LDL, TGs; **Hematology**: standard panel including complete blood count with automated differential including platelets, and coagulation panel INR, and Hep A (HAVIgM) test at screening, and **Inflammatory markers** (e.g. CK-18, TNF α , IL-6) will be analysed by a central lab.

Fatty acid analyses and analyses of LC-PUFA-derived oxylipins will be performed using plasma samples at the DSM Clinical Laboratory, [name]. Approximately 1.5 mL of plasma/subject/time point (V1, V3, V4) will be aliquoted and shipped frozen on dry ice in batches from the central lab to DSM.

500uL plasma for α -tocopheryl measurement (from V1, V3, V4) will be shipped frozen on dry ice in batches from the central lab to DSM Nutritional Products:

DNP R&D Analytics, NIC-RD/A Sample Registration Office, c/o Warenannahme, [name] Phone: [name] Fax: [name]

Transcriptome analysis of Gene Expression: in a subset of 40 subjects (~10 subjects/treatment arm), whole blood (~2ml) will be collected in PAXgene blood RNA tubes. Samples will be collected at Screening V1 and at Visit 4 and will be shipped frozen using dry ice along with other blood samples to the central lab the day it is drawn. Samples will be batched shipped frozen from the central lab to DSM Nutritional Products, Kaiseraugst, Switzerland for analysis.

Genotype analyses

An aliquot of whole blood (0.5ml) from each subject will be used for DNA extraction to identify those with single-nucleotide polymorphisms (SNP) i.e. PNPLA3, HSD17b and haptoglobin. Samples will be collected at Screening V1 and will be shipped frozen using dry ice along with other blood samples to the central lab the day it is drawn. Samples will be batched shipped frozen from the central lab to Indiana University for analysis.

An additional 1 ml plasma (aliquoted into [2] 0.5ml tubes) will also be collected at V1 and V4, shipped frozen on dry ice to central lab and stored for future NAFLD biomarker use.

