8 EARLY SUBJECT WITHDRAWAL

Subjects have the right to withdraw from the study at any time for any reason, without being obliged to give reasons and without penalty or loss of benefits to which they are entitled. The investigator also has the right to withdraw subjects from the study if this is in the best interest of the subject.

Any of the following conditions leads to premature withdrawal:

- request by subject to discontinue for any reason during the study (withdrawal of consent)
- erroneously included / randomized subject
- adverse event or concurrent illness that, in the opinion of the investigator, warrants the subject's withdrawal from intervention
- intake of concomitant medications/dietary supplements prohibited by the protocol
- volunteers who do not follow the requirements of the investigator, especially those concerning safety and/or if the subject, after his enrolment is uncooperative or not willing to comply with the protocol (non-compliant)
- failure to return (lost to follow-up)
- request by the Sponsor or regulatory agencies for termination of supplementation of an individual patient or all patients under this protocol
- pregnancy, i.e. a protocol exclusion criterion

The circumstances of any discontinuation must be documented in detail in the corresponding study disposition form in the eCRF. Whenever a subject is withdrawn from the study for whatever reason, every effort will be made to perform a final assessment to include standard medical and laboratory tests (**including a final MRI, if possible**) which would have been done upon normal completion of the study, i.e. V4. The data of the withdrawn subjects will be documented in the clinical study report and may be used in statistical analyses.

Note: Subjects who withdraw prematurely from the study will not be replaced.

Protocol no.: 2017-	Version:
1088	3

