10.3.3 Responsibilities

- The Principal Investigator (PI) ensures that SAE reporting procedures outlined in the study protocol are adhered to and that all required documentation is up-to-date and that regulatory and IRB/IEC SAE reporting procedures are followed.
- All study personnel at the study sites (Study Coordinator, Study Nurse, PI, or designee) who are in contact with clinical trial subjects are responsible for collecting AE information from the subject at each scheduled site visit or during telephone calls with the subject. Therefore, clinical research personnel or delegates (e.g. CRO) who initiate and monitor the study are responsible for explaining the procedures for reporting and evaluating AEs to the PI, and all study personnel who will be in contact with the subjects/patients.
- During the course of the study complete reports of all AEs should be entered in the subject's/patient's site source documents, and on the appropriate study case report forms (CRFs).
- A physician is responsible for: identifying and evaluating the severity (mild, moderate, or severe) and clinical importance of the AE, taking appropriate medical action(s), and for notifying a clinical research monitor, CRO and PV vendor immediately of an SAE, as specified in the protocol, and also for notifying the IRB/IEC. A copy of the source documents and related records should be supplied with the SAE report to the PV Vendor.
- Likewise, a physician indicates the causality (relationship) of the AE to the study product.
- For any laboratory abnormality, the PI will make a judgement as to its clinical significance. If the laboratory value is thought to be clinically significant, the IND Sponsor or medical monitor may be consulted, and an assessment will be made by the PI, as to its relationship to investigational product administration, and it will be documented on the AE page of the eCRF.

- The PI should comply with applicable regulatory requirement(s) related to the reporting of SAEs to the regulatory authority(ies) and the IRB /IEC.
- At completion of the study, the final lists of AEs and SAEs will be MedDRA coded by the CRO or PV vendor.

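### The DILI table gives no instruction when ALT meets a repeat-test or interrupt trigger, total bilirubin is above normal and the subject has no listed symptom

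*Protocol*

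**What the plan says.** The table in Protocol 10.3.2 pairs an ALT trigger, a bilirubin state and a symptom state with an action. Its rows are not numbered; here they are numbered 1 to 5 in printed order.

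- Rows 1 and 3 are the only rows with no symptoms. Row 1 asks for repeat liver tests within 2 to 5 days. Row 3 interrupts drug; its trigger for raised entry ALT is "Elevated baseline: ALT ≥5x baseline or ≥500 U/L whichever occurs first". In both, the bilirubin cell reads "Normal Patients with Gilbert's syndrome: No change in baseline total bilirubin". Row 2 has the same bilirubin cell but requires symptoms.
- Rows 4 and 5 interrupt drug. Row 4 needs total bilirubin of at least 2x ULN, or its Gilbert's criterion, "Patients with Gilberts syndrome: Doubling of direct bilirubin or increased INR to >1.5". Row 5 accepts normal or raised bilirubin. Both require an item from the symptom list, which includes eosinophilia above 5%.

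The month 3 visit (Protocol 6.4.3) specifies "Fasted Blood draws (>10 hours) for Clinical chemistry, CBC, Fatty Acid (DHA) and Vitamin E analyses". It is the only scheduled on-treatment chemistry before month 6. Protocol 7.1.3 defines the haematology panel as a "complete blood count with automated differential including platelets", so eosinophilia would be seen there.

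**The concern.** ALT and bilirubin rising together is a worse liver picture than ALT alone, and the table itself treats bilirubin as aggravating. Rows 2 and 4 share the same ALT triggers and symptom list, and bilirubin of at least 2x ULN moves the action from repeat tests to interruption. Without symptoms the direction reverses: raised bilirubin takes the subject out of rows 1 and 3, and no other row takes them in.

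At stake is a subject-level safety instruction. A site that reads the chart row by row at month 3 would find an explicit action for the milder result and none for the worse one. With about 16 planned sites (Protocol 4.5), the response could vary from site to site.

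**Working it through.** There is no plan figure to reproduce. The check is to set out the five rows and see which ones each clinical picture matches. Let b be an elevated baseline ALT in U/L.

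| Row | ALT, normal or near-normal baseline | ALT, elevated baseline | Bilirubin | Symptom or eosinophilia | Action |
|---|---|---|---|---|---|
| 1 | ≥5x ULN | ≥ min(3b, 300) | normal | none | repeat |
| 2 | ≥3x ULN | ≥ min(2b, 300) | normal | yes | repeat |
| 3 | ≥8x ULN | ≥ min(5b, 500) | normal | none | interrupt |
| 4 | ≥3x ULN | ≥ min(2b, 300) | ≥2x ULN | yes | interrupt |
| 5 | ≥5x ULN | ≥ min(3b, 300) | normal or raised | yes | interrupt |

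In Gilbert's syndrome, normal in rows 1 to 3 is replaced by no change in total bilirubin, and row 4 uses its own criterion.

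**Two elevated baselines, no symptoms.** Entry ALT must be at least 40 and below 250 U/L, so both are possible.

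- b = 60: row 1 starts at min(180, 300) = 180 and row 3 at min(300, 500) = 300.
- b = 80: row 1 starts at min(240, 300) = 240 and row 3 at min(400, 500) = 400.

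These instructions hold with normal bilirubin. With bilirubin above normal, whether below or above 2x ULN, no row matches at any ALT. The same is true for a normal baseline at 5x, 8x or 10x ULN.

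**Bands for subjects without Gilbert's syndrome.** Call the ALT bands A (from the row 2 and 4 trigger), B (from the row 1 and 5 trigger) and C (from the row 3 trigger). For a normal baseline these are 3 to <5x, 5 to <8x and ≥8x ULN. Cross them with two raised-bilirubin levels (above ULN but <2x ULN; ≥2x ULN) and symptoms yes or no: 3 x 2 x 2 = 12 states.

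- No symptoms, B, both bilirubin levels: no row; row 1 repeat would apply with normal bilirubin (2 states).
- No symptoms, C, both levels: no row; row 3 interrupt would apply with normal bilirubin (2 states).
- Symptoms, A, bilirubin <2x ULN: no row; row 2 repeat would apply with normal bilirubin (1 state).
- No symptoms, A, both levels: no row, but none with normal bilirubin either (2 states, nothing lost).
- Remaining 5 states, all with symptoms: row 4 or 5 applies.

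So 2 + 2 + 1 = 5 of 12 states lose an instruction. The symptomatic one is the smaller gap: ALT 3 to <5x ULN, or 2 to <3x an elevated baseline and below 300 U/L. When b is at least 150, 2b reaches 300 and band A is empty, leaving 4 of 8.

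**Timing.** A row 3 hold ends only when another cause is found and enzymes are back at baseline. The gap therefore arises when raised bilirubin is present at or before the time ALT meets the trigger, including in the same sample.

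**The case against.** The strongest reply is that the chart offers guidelines and management recommendations to experienced hepatology clinics, and that no sensible reader would continue drug at ALT ≥8x ULN because bilirubin was also raised. Judgement is also required elsewhere. Protocol 10.3.3 has the investigator assess every laboratory abnormality and a physician act on adverse events. Protocol 8 lists as grounds for withdrawal an "adverse event or concurrent illness that, in the opinion of the investigator, warrants the subject's withdrawal from intervention". This stands as far as it goes: the duty to act remains. But those sections give no threshold, repeat interval or restart condition, which is what a section on holding and stopping rules is for. SAE reporting (10.3.1) and the DSMB stopping rules (10.3.2) do not hold drug in an individual subject.

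Four stronger readings are tempting, and the documents do not support them.

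- A reader might infer that a bilirubin rise cancels a hold. It does not; row 3's restart condition continues to bind.
- A reader might infer that any rise opens the gap. Outside Gilbert's syndrome, a rise within the normal range still meets rows 1 and 3.
- A reader might double the state count for Gilbert's syndrome. Rows 1 to 3 look only at total bilirubin, so a Gilbert's subject with INR above 1.5 and unchanged total bilirubin, without symptoms, still matches row 1 or 3. The count depends on whether total bilirubin also changes. INR is scheduled only at screening.
- A reader might take the state count as a risk. It counts table cells, not patients.

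**Conclusion.** The gap is real and should be fixed. Without a listed symptom or eosinophilia above 5%, a subject whose ALT meets a row 1 or row 3 trigger while total bilirubin is above normal (Gilbert's: changed from baseline) has no table instruction, although the same ALT with normal bilirubin has one. The narrower symptomatic gap below row 4's bilirubin criterion is also real.

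This rests on reading the cells as printed; the symptom requirement is in row 4's own cell. How many subjects would be affected cannot be estimated, because the documents give no ULN, event frequency, baseline ALT distribution or Gilbert's prevalence. What is missing is the specific rule. The documents do not direct sites to continue drug, and they do not remove the investigator's ability to stop it.

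**What to change.** Amend the table in Protocol 10.3.2 in three places.

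1. Apply row 4 (interrupt) with or without symptoms.
2. Let rows 1 to 3 apply at any bilirubin level that does not meet row 4's criterion, including Gilbert's subjects whose total bilirubin has changed without meeting it.
3. State that the most stringent matching row governs.

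Of the five states above, the two without symptoms at ≥2x ULN become interrupt under row 4. The two without symptoms below 2x ULN keep row 1 (repeat) in band B and row 3 (interrupt) in band C. The symptomatic one gets row 2 (repeat).

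This is more than a clarification. It creates a new hold for subjects without symptoms with ALT 3 to <5x ULN (or 2 to <3x an elevated baseline and below 300 U/L) who meet row 4's bilirubin criterion; today they have no action even with normal bilirubin. The cost is a few more drug interruptions and a protocol amendment, which goes to the IRB and, as required, FDA before it takes effect (Protocol 11.4 and 12.1). Sample size and analysis do not change.
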